As of 14th February 2022, 2,500 adult solid organ transplant recipients have self-registered with the trial web portal and returned the results of the LFIA they received following their 3rd vaccine dose. Depending on availability of LFIA kits, participants who had an initial negative test will be further invited to perform an additional LFIA test, after receipt of their fourth or subsequent vaccine dose. These additional tests will provide data on the proportion of transplant recipients who seroconvert after their fourth or subsequent vaccine dose, despite being negative for anti-SARS-CoV-2 IgG antibodies after their third dose.

People with cancer and autoimmune disease: A random selection of eligible patients with autoimmune disease or haematological malignancy registered on the NCARDRS and NCRAS databases respectively, will be invited to join the study via personalised letter. Up to 2 reminders will be sent to potential participants. Patients responding to the invitation will register via the Ipsos MORI web portal. Using the experience from REACT-2, we estimate a response rate of 70% at registration and 85% at lateral flow test completion.

Following registration on the web portal and completion of a short online questionnaire including information on immunosuppression and medical history, sociodemographic variables and COVID-19-related behaviours and COVID-19 infection history, participants will be sent a LFIA test, which is provided with a detailed instruction booklet and link to an instruction video. For consenting young persons aged 12-15, the LFIA kit will be addressed to the parent / guardian whose name they have provided. Participants will be asked to carry out the test and follow the instructions to read the result and to take a photograph of the completed test, if possible. They will then provide their results via the web portal. A telephone helpline will be established to deal with any queries that may arise. Usability of the test has been assessed in REACT-2 study.

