7. STATISTICS AND DATA ANALYSIS

Data collection will be undertaken in collaboration with implementation partner Ipsos MORI. The data from the participants is self-entered into an online questionnaire hosted on a secure web portal developed and managed by Ipsos MORI.

Ipsos MORI will be responsible for setting up and managing the study web portal, receiving the questionnaire data, setting up and entering the questionnaire data into the study database and linking in the uploaded results of lateral flow assay. Once data is complete, a copy of the study database for each patient population will be sent securely from Ipsos MORI to NHSBT and NDRS where it will be linked to routinely collected healthcare data on COVID-19 infection, and severe outcome over the subsequent 6 months and analysed.

Analysis for the a) solid organ transplant groups and b) rare autoimmune disease and cancer groups will be conducted using a common protocol and statistical analysis plan, but separately by NHSBT and NDRS respectively, due to the complexities of data sharing between the two registries and existing restrictions on the data sharing they have with NIMS and NHS Digital. The high-level analysis plan is as follows:

1. The proportion of patients (and 95% CI) with and without antibodies to SARS-CoV-2 at least 21 days post 3rd vaccine and prior to 4th vaccine dose will be presented.
2. The proportion of patients (and 95% CI) with and without antibodies to SARS-CoV-2 following a 4th vaccine dose will be presented
3. The cumulative incidence (and 95% CI) of participants having at least one RT-qPCR proven infection in the 6-month follow-up will be presented for those with and without antibodies to SARS-CoV-2 at the time the study LFIA was undertaken. Risk-adjusted cumulative incidence rates will be compared using a Fine and Gray model. These methods allow for participants who may die during the follow-up period.
4. The cumulative incidence (and 95% CI) of participants hospitalised due to COVID-19 and deaths due to COVID-19 by 6 months will be presented for those with and without antibodies to SARS-CoV-2 at the time the study LFIA was undertaken and compared as described above if there are sufficient events.
5. Rates of those with and without antibodies to SARS-CoV-2 after 3rd or 4th vaccine (and 95% CI) will be presented for different clinical characteristics and

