sociodemographic factors. Logistic regression models will be used to identify which of these factors are independently associated with developing antibodies following completion of the primary vaccine course.

6. The proportion of re-sampled transplant recipients (and 95% CI) with and without antibodies to SARS-CoV-2 following 4th dose who did not have antibodies after 3rd dose.

All outcomes will be adjusted for other known risk factors, and receipt of a subsequent 4th vaccine dose, as and where appropriate. Multiple imputation based on full conditional specification will be used to impute values of potential risk adjustment factors. The set of variables that will feature in the multiple imputation models will be described in the SAP. Sensitivity analyses will be conducted with cases with missing primary outcome data excluded.

A descriptive analysis aligned with above will additionally be performed for the young adult population.

Sample size

Each participant population will recruit 12,000 participants, and of these, we expect 85% to return their LFIA result (n=10,200). Following a third vaccine, we estimate approximately a third of participants in each group will have no SARS-CoV-2 antibodies, so this sample size will give a 95% confidence interval for the proportion of participants with no antibodies of $\pm 0.91\%$ for each participant group ^{7,8}. Even if the proportion of participants with no antibodies is 50%, the confidence interval would be $\pm 0.97\%$, so the large study size gives very good precision.

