The lateral flow device to be used is the Fortress COVID-19 Total Antibody Device for the detection of IgM and IgG SARS-CoV-2 against the spike protein. The device has been evaluated for use in detecting anti-S in transplant patients and found to have a sensitivity of 92% and specificity of 95%¹³. The sample size calculation is described previously. The event rate of freedom from infection at 6 months in the group with antibodies was estimated from data in the PHE report "COVID-19 vaccine surveillance report - week 37". Table 2 of this report presents case rates per 100,000 for those who have received 2 doses of vaccine, which we have taken as our best estimate for event rates in a group with SARS-CoV-2 antibodies. The age-adjusted mean event rate from this data shows a 0.79% infection rate over a 4 week period in August 2021. Multiplying this up for our 6-month (180 day) follow-up period would suggest an event rate of 5.08%. However, this data relates to the UK population at large, not the higher risk immunosuppressed population that will be recruited to MELODY. Recent data on COVID-19 infection among those with rare autoimmune rheumatic disease showed that the age-standardised infection rate in this group was 1.54 times higher than in the general population¹⁷. We have therefore inflated our anticipated event rate by 50% to give the final event rate of 7.62% for this group (freedom from infection rate of 92.4%). Using the same process for the PHE data on unvaccinated individuals would suggest an infection rate 2.12% higher in the group with no SARS-CoV-2 antibodies. We have therefore powered the study to detect a 2% difference between those with and without antibodies. The statistical design and analysis was developed with co-applicants [name], [name] and [name].

1. JCVI advice on the UK vaccine response to the Omicron variant.
2. Kamar, N., et al. Assessment of 4 Doses of SARS-CoV-2 Messenger RNA-Based Vaccine in Recipients of a Solid Organ Transplant. *JAMA network open* **4**, e2136030 (2021).

3. Caillard, S., *et al.* Antibody response to a fourth mRNA Covid-19 vaccine boost in weak responder kidney transplant recipients. *medRxiv*, 2021.2009.2003.21262691 (2021).
4. Qin, C.X., *et al.* Antibody response to 2-dose SARS-CoV-2 mRNA vaccination in pediatric solid organ transplant recipients. *American Journal of Transplantation* **22**, 669-672 (2022).

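### Items 5 and 6 are read as vaccine response, but the anti-spike test cannot exclude infection antibody, and the infection history collected is not named in either analysis

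*Combined protocol and SAP*

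**What the plan says.** Appendix 1 describes the device as one "for the detection of IgM and IgG SARS-CoV-2 against the spike protein". Section 4.2 sets eligibility by patient group, age and three vaccine doses, and does not exclude people with an earlier infection.

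The information on earlier infection exists. Under section 4.3, the questionnaire completed before the kit is sent covers "COVID-19-related behaviours and COVID-19 infection history". Section 4.2 describes registry linkage that supplies RT-qPCR infections.

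Four items in section 7 use the antibody result as an outcome:
- Item 1 gives the proportion "with and without antibodies to SARS-CoV-2 at least 21 days post 3rd vaccine and prior to 4th vaccine dose will be presented", and item 2 does the same after the 4th dose.
- Item 5 tabulates antibody status by clinical and sociodemographic factors, then uses logistic regression to find those "independently associated with developing antibodies following completion of the primary vaccine course".
- Item 6 gives the proportion of re-sampled transplant recipients with antibodies "following 4th dose who did not have antibodies after 3rd dose". Section 4.3 describes the purpose of this re-test as showing how many seroconvert after that dose.

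None of these names prior infection as a restriction, stratum, covariate or sensitivity analysis. A general clause in section 7 says that outcomes will be adjusted for other known risk factors where appropriate. The only factor it names is a later 4th dose. Section 7 explicitly leaves to the SAP only the variables for the imputation models.

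**The concern.** A person can be anti-spike positive because of vaccination, infection or both. The documents do not say this outright, but it follows from the device's target, since spike is a protein of the virus. A positive result therefore shows serostatus and not its source.

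This matters where the result is given a vaccine-response meaning. In item 6, someone who is negative after dose 3, is infected, and is then positive at the re-test counts as a dose-4 seroconversion. In item 5, a factor that changes exposure to infection can look like a factor that changes vaccine response. Section 1.1 supplies the mechanism: it notes that many patients still shield, so exposure differs between participants.

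Section 1.1 wants the results to support stratified advice and to identify patients who might benefit from other prophylaxis. Factors picked up through exposure would mislead both uses. The transplant registry and the disease registration service analyse their groups separately, so each could also treat an unnamed covariate differently.

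**Working it through.** **1. The plan's own precision.** Inputs from section 7: 10,200 results per group (85% of 12,000), and "we estimate approximately a third of participants in each group will have no SARS-CoV-2 antibodies". The half-width is 1.96 × √(p(1−p)/n).
- p = 1/3: 1.96 × √(0.3333 × 0.6667 / 10,200) = 0.915 points (stated: 0.91).
- p = 0.5: 0.970 points (stated: 0.97).

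Both figures reproduce, so there is no arithmetic error here.

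**2. Gap between the overall and the infection-free proportion.** Let q be the share infected before the test, s the seropositivity among them, and v the seropositivity in the rest. The overall proportion is q·s + (1−q)·v, so the gap is q(s − v). The documents give neither q nor s. Assumed: q = 5-20%, s = 90-95%, v = 60-66.7%.

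| q | Smallest gap, s − v = 0.90 − 0.667 | Largest gap, s − v = 0.95 − 0.60 |
|---|---|---|
| 5% | 1.2 points | 1.75 points |
| 10% | 2.3 points | 3.5 points |
| 20% | 4.7 points | 7.0 points |

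Two checks on s:
- Section 7 gives a device sensitivity of 92.0%. Capping s at 92% lowers the largest gaps to 0.05 × 0.32 = 1.6, 0.10 × 0.32 = 3.2 and 0.20 × 0.32 = 6.4 points.
- With s = 80% and v = 66.7%, q = 5% gives 0.05 × 0.133 = 0.7 points, which is below 0.91.

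**3. Item 6.** Section 7 plans for 90.4% infection-free at six months without antibodies, so 9.6% infected. Assume three months between tests, which gives half of that, 4.8%. Section 1.1 cites a de novo response to dose 4 of up to 42%; take v = 42%.
- s = 90%: 0.048 × (0.90 − 0.42) = 2.3 points.
- s = 95%: 0.048 × (0.95 − 0.42) = 2.5 points.
- s = 80%: 0.048 × (0.80 − 0.42) = 1.8 points.

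People still negative after three doses may also respond poorly to infection, so s is especially uncertain here. In the other direction, section 7 expects Omicron to raise infection rates.

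The number re-tested is not fixed. If a third of the 2,500 recipients in section 4.3 were negative and all were re-tested (833), the half-width would be 1.96 × √(0.42 × 0.58 / 833) = 3.4 points. With a third of 10,200 (3,400) it would be 1.7 points. The shift is therefore of the same order as the sampling error of item 6, and a larger sample would not reduce it.

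**4. Item 5.** Take a factor with no effect on vaccine response whose two levels have q = 10% and q = 20%, with s = 95%.
- v = 60%: positive 0.635 against 0.670; odds ratio (0.670/0.330)/(0.635/0.365) = 1.17.
- v = 65%: positive 0.680 against 0.710; odds ratio (0.710/0.290)/(0.680/0.320) = 1.15.

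With q = 10% against 30%, the same formula gives 1.37 and 1.34. These apply if prior infection is left out of the model.

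**5. Precision after restriction.** If 66.7% are positive overall, the infection-free proportion is (0.667 − q·s)/(1 − q). At q = 10% and s = 90-100% it is 64.1-63.0% with n = 9,180, and the half-width is 0.98-0.99 points. At q = 20%, n = 8,160 and it is 1.06-1.07 points.

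**The case against.** The strongest reply is that the study measures serostatus. Section 4.1 calls it a seroprevalence survey, and the first two objectives in section 2 concern detectable antibodies following a dose. For that quantity items 1 and 2 are right whatever the source of the antibody, and restricting them would answer a different question. This stands. A reader might infer that the plan attributes every positive result to vaccination, or that items 1 and 2 are biased. The documents do not support either reading, and the gap in step 2 is not an error in seroprevalence.

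Second, adjustment is promised. Section 7 describes a high-level plan with adjustment for known risk factors, and infection history is collected alongside the other covariates. Item 5 may therefore be covered in practice. This stands in part: the clause does not name prior infection, and it cannot change a raw proportion such as item 6.

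Third, a reader might infer that prior infection confounds item 3 by a calculable amount. The documents do not support that either. Item 3 specifies risk-adjusted comparison by a Fine and Gray model, and Appendix 1 promises adjustment for important confounders. An unadjusted illustration would not size the bias of that analysis.

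Fourth, every magnitude rests on assumed inputs. This also stands. Section 1.1 reports weak vaccine immunogenicity in these patients, so 90% seropositivity after infection is not assured.

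**Conclusion.** The point holds for items 5 and 6. Their wording and stated purpose are vaccine response, the test cannot show where antibody came from, and the available infection data are not named in the analysis. Item 6 is the clearer case, because an infection between the two tests is counted as a dose-4 response and no adjustment clause can remove it. For item 5 the weakness is an unnamed covariate that the analysts may or may not include.

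The size is conditional. Over the assumed ranges the shift in a proportion is about 1.2-7.0 points, falling to about 0.7 at the lower seropositivity shown. For item 6 it is roughly 1.8-2.5 points on the plan's pre-Omicron rate and an assumed three-month gap. A spurious odds ratio of about 1.15-1.17 in item 5 needs a 10-point difference in infection share and no adjustment for it.

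**What to change.** State in the analysis plan, for both analysing registries:
- **Item 6:** report the proportion overall, and in those with no recorded or self-reported infection before the second test, including between the two tests.
- **Item 5:** include known prior infection (self-report, or linked RT-qPCR before the test) as a covariate in the logistic model, and repeat the model in participants without known prior infection.
- **Items 1 and 2:** keep the all-participant seroprevalence as the main figure and add a breakdown by known prior infection.
- **Item 3:** list prior infection among the risk-adjustment factors already promised.

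The cost is some wording, about one extra table and slightly wider intervals in the restricted estimates (step 5). The linked data suffice for infections between tests. The documents describe no second questionnaire, so self-report for that interval would need a question at the re-test.

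Two limits remain. Undetected infections cannot be removed, so the restricted figures reduce the problem without ending it. Infection after vaccination may also be commoner in poor responders, as section 1.2 hypothesises, so excluding the infected could remove some non-responders. The overall and restricted figures should therefore be shown together.

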13. APPENDIX 1. REPRODUCIBILITY AND STATISTICAL DESIGN ANNEX

This is an observational cohort study which will recruit 12,000 participants to each of 3 patient populations - 36,000 in total. We anticipate a LFIA result return rate of 85%, giving data on 10,200 cases in each participant population. Participants will either be invited at random to participate (autoimmune and cancer), or sign-up themselves (transplant), minimising potential recruitment bias, although self-selection bias could occur for either approach. This can be assessed by comparing those recruited against wider data on the registries participating in the study, and risk adjustment for any important confounders associated with outcome will be conducted.

LFIA diagnostic accuracy.

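### The only stated check for missing outcomes does not test the expected 15% LFIA non-return, which is left unexamined for the antibody proportions

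*Combined protocol and SAP*

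**What the plan says.** On missing data, Section 7 states: "Multiple imputation based on full conditional specification will be used to impute values of potential risk adjustment factors". It leaves one detail for later: "The set of variables that will feature in the multiple imputation models will be described in the SAP". The next sentence is the only missing-outcome check in the document: "Sensitivity analyses will be conducted with cases with missing primary outcome data excluded".

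On non-return, the sample size text in Section 7 says: "Each participant population will recruit 12,000 participants, and of these, we expect 85% to return their LFIA result (n=10,200"). Appendix 1 repeats this: "We anticipate a LFIA result return rate of 85%, giving data on 10,200 cases in each participant population". For the antibody result itself, Section 7 says: "we estimate approximately a third of participants in each group will have no SARS-CoV-2 antibodies". From these it derives a 95% interval of ±0.91 points per population.

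On what is known about non-returners, Section 4.3 places registration and "completion of a short online questionnaire including information on immunosuppression and medical history" before the kit is sent.

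**The concern.** Analysis items 1 and 2 in Section 7 are simple proportions of people with and without antibodies. A registrant who returns no LFIA has no value for that outcome. The plan does not say that such a person enters the main estimate by imputation, weighting or any other route, and the precision figure uses returners as its denominator. A sensitivity analysis that drops people with a missing outcome would then drop people who were never counted.

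The stake is the study's first two objectives. The quoted interval reflects sampling error only. Return of the kit may relate to illness, age or expected response; the documents do not say whether it does. If it does, the returner proportion is off for registrants as a whole. The planned check cannot show this, because for these items it agrees with the main estimate whatever the non-returners' status.

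**Working it through.** **Inputs.** From Section 7 and Appendix 1: 12,000 recruited per population and 85% return, so 12,000 × 0.85 = 10,200 returners and 1,800 non-returners; about one third negative. The proportion negative among non-returners, *q*, is not in the documents and is varied as an assumption. The arithmetic treats each population as one group, as the plan's own sample size does, without splitting by third or fourth dose.

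**Step 1: reproduce the plan's precision.** Half-width = 1.96 × √(p(1 − p)/n).
- p = 1/3, n = 10,200: 0.915 points (0.913 at p = 0.33), against ±0.91 stated.
- p = 0.5, n = 10,200: 0.970 points, against ±0.97 stated.

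The figures reproduce with n = 10,200, so the planned proportion is one among returners.

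**Step 2: the planned sensitivity analysis, items 1 and 2.**
- Main estimate: 3,400/10,200 = 33.3%.
- After excluding registrants with no LFIA result: 3,400/10,200 = 33.3%.

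**Step 3: the same check if the primary outcome is infection.** In item 3 antibody status is the exposure, and infection comes from linked records. A registrant without an LFIA result lacks the exposure. Excluding people with missing infection data neither brings that registrant in nor shows what the absence does.

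**Step 4: what non-return could do to the proportion.** Share negative among all registrants = (3,400 + 1,800 × *q*)/12,000.

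| Assumed *q* | Calculation | All registrants | Returner estimate of 33.3% is |
|---|---|---|---|
| 20% | 3,760/12,000 | 31.3% | 2.0 points too high |
| 1/3 | 4,000/12,000 | 33.3% | unbiased |
| 40% | 4,120/12,000 | 34.3% | 1.0 point too low |
| 50% | 4,300/12,000 | 35.8% | 2.5 points too low |
| 60% | 4,480/12,000 | 37.3% | 4.0 points too low |

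The logical limits are 3,400/12,000 = 28.3% (*q* = 0) and 5,200/12,000 = 43.3% (*q* = 100%). They need every non-returner to be positive or every one negative, so they are bounds and not expectations.

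**Step 5: when this matters.** The bias is 0.15 × (*q* − 1/3). It equals 0.91 points when *q* differs from one third by 0.91/0.15 ≈ 6.1 points, that is at about 39.4% or 27.3%. Between those values it stays inside the stated interval.

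**The case against.** The plan never calls its main analysis complete-case. Labelling the exclusion a sensitivity analysis could imply that the main analysis keeps people with missing outcomes, perhaps because the outcome is itself imputed. Section 7 describes itself as high-level and points to a SAP for detail. Since no outcome is named primary and the power calculation concerns RT-qPCR infection, the sentence may be about infection. Missing data would then mean failed linkage or withdrawal, and excluding those people could change the Fine and Gray result. Appendix 1 also acknowledges self-selection and plans a registry comparison and risk adjustment.

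Much of this limits the point. Returner-only handling is an inference from covariate-only imputation and the 10,200 denominator. A reader might infer that the exclusion is empty for every outcome; the documents do not support that, because for infection and hospitalisation it may be informative. A reader might also infer that the antibody estimate will be biased beyond its interval; the documents give no antibody rate for non-returners, and a difference under about 6 points would not do it.

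The gap remains all the same. Only the list of imputation variables is deferred, not what is imputed or how non-return is examined. The Appendix 1 comparison sets those recruited against the registries, whereas non-return happens after recruitment; risk adjustment of associations does not put non-returners back into a proportion. Even if outcomes were imputed, comparing the result with returners alone would not test non-return that depends on antibody status.

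**Conclusion.** The point holds for the antibody proportions. As written, the stated check repeats the main estimate for items 1 and 2. If infection is the outcome meant, it still does not reach registrants without an LFIA result. The expected 15% non-return is therefore untested on either reading.

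The direction and size of any bias are unknown. Over assumed non-responder rates of 20% to 60% negative, the share among registrants runs from 31.3% to 37.3%, against 33.3% in returners. The stated ±0.91 points is exceeded only above about 39.4% or below about 27.3%. This rests on the plan's own 85% return and one-third negative, and on reading the main estimate as returner-only. The study design and its sample size figures are not in question.

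**What to change.** Name the primary outcome and say how a missing LFIA result enters each analysis. Keep the exclusion analysis for the infection outcomes only. For items 1 and 2, and the descriptive rates in item 5, add:

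- **Inverse-probability-of-return weighting among registrants.** Model return on the questionnaire completed before the kit is sent, plus registry variables where non-returners are linked. Section 7 sends the database for linkage once data are complete and does not say whether non-returners' records are included, so this needs stating. Assign non-returners to the third-dose or fourth-dose group by vaccine status at kit dispatch.
- **A two-sided delta analysis.** Let non-returners be both less and more often negative than weighted returners, for example from −30 to +30 points, with the limits declared as assumptions. At 15% non-return this moves the proportion by up to 0.15 × 30 = 4.5 points either way. Report the delta at which the bias passes ±0.91 points.

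The cost is SAP wording, a little more analysis and slightly wider intervals; the questionnaire data are already planned. The weighting corrects for non-return among registrants only. It does not correct for non-registration, which the Appendix 1 registry comparison must still address.

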The study has been powered to detect a difference of 2% in the proportion of participants free from RT-qPCR proven infection in the 6-month follow-up period, with 90% power and a 5% two-sided significance level. We have assumed a 2:1 ratio between those with and without SARS-CoV-2 antibodies, as described above. In the group with SARS-CoV-2 antibodies it has been estimated that 92.4% will be free from infection at 6 months and to detect a decrease to 90.4% in the group without SARS-CoV-2 antibodies using survival analysis methods, we require 9,273 participants in total in each participant population (justification for the expected rate is provided in Appendix 1 (Reproducibility statistical and design annex)). Our planned recruitment of 10,200 LFIA results per group therefore allows for up to a 9% withdrawal rate, which we think is very achievable as patients will have opted-in to the study initially. Higher LFIA return rates, a lower withdrawal rate, or combining data across the patient populations would enable smaller differences to be detected. We think that the timing of the study, and early evidence of strong engagement, would mean that only a relatively small number of patients would have received their 4th dose at the time of recruitment. With the emergence of Omicron, we expect infection event rates observed in the study to now be higher than those used in the original sample size calculation, even if the 4th dose reduce rates of RT-qPCR positive infection.

DIAGNOSTIC ACCURACY OF THE IMMUNOASSAYS

Using the threshold value for positivity on serological testing of ≥ 7.10 BAU/ml (n=183) on Abbott Architect Assay and confirmatory DABA results for available discordant samples (n=3) as the reference standard, the overall performance of the test in these combined cohorts produce an estimate of sensitivity of 92.0% (115/125; 95% CI 85.8% to 96.1%) and specificity of 95.1% (58/61; 95% CI 86.3% to 99.0%).

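### The ±0.91% and ±0.97% half-widths are sampling error of the LFIA result but are worded as precision for having no antibodies, and the plan makes no use of the test accuracy it reports

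*Combined protocol and SAP*

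**What the plan says.** The sample size text in section 7 expects 10,200 LFIA results per population and about one third of participants without antibodies. It states that "this sample size will give a 95% confidence interval for the proportion of participants with no antibodies of" ±0.91%, and gives ±0.97% for the case where half have none.

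The power statement follows. The study is "powered to detect a difference of 2% in the proportion of participants free from RT-qPCR proven infection", with 90% power at 9,273 per population, a 2:1 ratio, and 92.4% against 90.4% infection-free. Appendix 1 takes the first rate from people with two vaccine doses, "which we have taken as our best estimate for event rates in a group with SARS-CoV-2 antibodies", and bases the 2-point difference on unvaccinated people. Analysis 3 compares infection "for those with and without antibodies to SARS-CoV-2 at the time the study LFIA was undertaken".

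The accuracy paragraph at the end of section 7 gives "sensitivity of 92.0% (115/125; 95% CI 85.8% to 96.1%) and specificity of 95.1% (58/61; 95% CI 86.3% to 99.0"%. The comparator is an Abbott assay threshold with "confirmatory DABA results for available discordant samples (n=3) as the reference standard". Appendix 1 repeats the two point estimates.

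Section 2 defines objectives 1 and 2 by LFIA result. Section 4.3 says that transplant recipients with a negative first test may be re-tested after a later dose, and describes a later positive as seroconversion. Analysis 6 reports the re-test proportion.

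**The concern.** A 95% interval of under one point either way is correct for the share who test LFIA-negative. It is not an interval for the share without antibodies, because the test misreads some people in each direction and its error rates are themselves estimated from only 125 and 61 samples. Recruiting more participants does not reduce that part of the uncertainty. The plan reports the error rates but does not carry them into its precision, its power or its listed analyses. The one sensitivity analysis it names concerns missing outcome data.

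A reader could therefore take the raw LFIA-negative share as the share without antibodies to within a point. The infection comparison has a similar gap: the plan does not say whether its 2-point difference is between LFIA-defined groups or between groups by reference antibody status. In the re-test analysis, participants are selected on a negative first result, so some first negatives may be false negatives, and a later positive from one of them could be credited to the extra dose.

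**Working it through.** **Inputs (section 7).** n = 10,200 results; share without antibodies q = 1/3 or 1/2; Se = 115/125 = 0.920; Sp = 58/61 = 0.951; 6-month infection risks 7.6% and 9.6%; N = 9,273.

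**1. Reproducing the stated figures.** Half-width = 1.96 × √(p(1−p)/10,200).
- p = 1/3: 0.0091
- p = 1/2: 0.0097

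Both match the plan and contain sampling error only. The exact binomial intervals for 115/125 and 58/61 also reproduce.

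**2. What the LFIA would show.** LFIA-negative share = q × Sp + (1−q) × (1−Se).
- q = 1/3: 0.333 × 0.951 + 0.667 × 0.080 = 0.370, a shift of +3.7 points
- q = 1/2: 0.500 × 0.951 + 0.500 × 0.080 = 0.515, a shift of +1.5 points

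Drawing Se and Sp jointly from Beta distributions (Jeffreys prior) gives 95% ranges of +0.1 to +7.6 points and −2.7 to +4.9 points. The shift is zero at q = 0.080/(0.080 + 0.049) = 0.62 and reverses above that.

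**3. Working back from an observed share.** Rogan-Gladen: adjusted share = (observed − (1−Se))/(Se + Sp − 1). With one third observed: (0.333 − 0.080)/0.871 = 0.291.

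The delta-method half-width combines three components, each 1.96 times a standard error. The adjusted negative share is 0.291 and the positive share 0.709.
- sampling: 1.96 × √(0.222/10,200)/0.871 = 1.05 points
- sensitivity: 1.96 × (0.709/0.871) × √(0.92 × 0.08/125) = 3.87 points
- specificity: 1.96 × (0.291/0.871) × √(0.951 × 0.049/61) = 1.81 points
- total: √(1.05² + 3.87² + 1.81²) = 4.4 points

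Beta draws give 24.0% to 33.3%.

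**4. Power.** For LFIA-defined groups with the stated inputs, the pooled-variance two-proportion formula gives (0.0200 − 1.96 × 0.00607)/0.00628 = 1.29, so power at 9,273 is 90.2%. The Schoenfeld formula (hazard ratio ln 0.904/ln 0.924 = 1.277) gives 89.1%. The stated 90% holds.

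Suppose instead that the inputs describe reference status and that test error is unrelated to infection risk. With one third reference-negative:
- NPV = 0.317/0.370 = 0.856 and PPV = 0.613/0.630 = 0.974
- LFIA-group risks are 9.31% and 7.65%
- difference = 2.0 × (0.856 + 0.974 − 1) = 1.66 points

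| Reading of the inputs | Two-proportion | Schoenfeld |
|---|---|---|
| All describe LFIA groups, 9,273 | 90.2% | 89.1% |
| All describe reference status, 9,273 | 79.5% | 78.4% |
| One third is LFIA-negative share, rates by reference status, 9,273 | 75.7% | 74.0% |
| All describe reference status, 10,200 | 83.1% | 82.1% |

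**5. Re-test analysis.** The share of LFIA-negatives who are reference-positive is 1 − NPV = 1 − 0.856 = 14% if one third are reference-negative (Beta draws 8% to 23%).

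**The case against.** The strongest reply is that the plan targets the LFIA result and says so. Objectives 1 and 2 are by LFIA testing, the precision sentence follows directly from the count of returned LFIA results, and accuracy is printed in the same section. That stands: the half-widths are right for the stated objectives, and the fault lies in the wording and in leaving the accuracy unused. Section 7 also calls itself a high-level plan and refers to an SAP for some detail, so an adjusted analysis may exist elsewhere. None is in the supplied text.

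Some stronger readings are tempting but unsupported:

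- **The study has only about 80% power.** The compared groups are set by the study LFIA, and the power paragraph counts LFIA results, so the text leans towards LFIA-defined groups. The event rates are vaccination-status proxies, neither LFIA nor reference status. The plan also expects higher infection rates with Omicron and mentions that "combining data across the patient populations would enable smaller differences to be detected", without figures for either.
- **The bias is always about four times the half-width.** That ratio (3.7/0.91) belongs to the one-third scenario. In the one-half scenario it is about 1.6 (1.5/0.97), with a range that spans zero.
- **About 14% of conversions after a fourth dose are spurious.** The 14% is a share of LFIA-negatives, not of conversions. Analysis 6 itself does not speak of seroconversion; that wording is in section 4.3.
- **The validation is in kidney transplant patients only.** Section 1.1 describes a kidney transplant cohort, but the accuracy paragraph refers to combined cohorts whose make-up is not given.

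**Conclusion.** The concern holds as a matter of labelling and of one missing sensitivity analysis. The stated half-widths are correct for LFIA positivity and too narrow for antibody status, where validation uncertainty dominates: about 4.4 points against 0.91 when one third test negative. These figures assume that the accuracy estimates apply in all three cohorts and to self-testing at home, and that the assay-threshold reference represents antibody status.

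A reader might infer a loss of power, but the documents do not establish one. The stated 90% is sound for LFIA-defined groups. Roughly 75% to 80% at 9,273 arises only if the inputs describe reference status and test error is unrelated to infection risk. No sample size, main analysis or study conduct needs to change. Severity: minor.

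**What to change.** - **Precision.** Label ±0.91% and ±0.97% as sampling error of LFIA positivity.
- **Analyses 1 and 2.** Keep the raw LFIA proportion as the main estimate. Add a sensitivity analysis with a proportion adjusted for sensitivity and specificity (Rogan-Gladen or Bayesian), whose interval carries the uncertainty from the 125 and 61 validation samples. State that the reference is an assay threshold and that applying the validation to all three cohorts is an assumption.
- **Power.** State that 90% at 9,273 is for a 2-point difference between LFIA-defined groups. The reference-status figures can be added as a conditional note, with their assumptions.
- **Re-testing.** In section 4.3, describe the outcome as LFIA conversion. For analysis 6, note that some first negatives may be false negatives (about 14% of LFIA-negatives if one third are reference-negative, range 8% to 23%).

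The cost is a few lines of wording and one sensitivity analysis from figures already in the protocol. The stated precision will look less favourable.
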